5.4 Screening and Subject Numbers

Each screened subject will be assigned a screening number consisting of "S" and the site number followed by a consecutive number starting with 01 at each site, e.g. S101, S102. The screening number shall be listed on a subject screening and inclusion log.

A "screening failure" is defined as a subject who does not fulfil the eligibility criteria. For screening failures, the eCRF screening visit shall be completed to an extent that makes it clear which assessments have been made and the reason why the subject did not fulfil the eligibility criteria. The reason for excluding a subject from entering the study shall also be specified in the subject screening and inclusion log.

 GALDERMA	Title 43CH1626 Clinical Study Protocol	Doc id MA-33281
--	--	---------------------------

Effective date: 2016-12-09 17:18

Effective

Version: 1.0

When the Investigator has confirmed that all inclusion criteria and no exclusion criteria are met, each enrolled subject will be assigned a subject number by the eCRF consisting of the site number followed by a consecutive number starting with 01 at each site, e.g. 101, 102.

The subject number, subject name, and other information sufficient to link the eCRF to the medical records (e.g. national identification number, chart number, etc.) shall be recorded on a subject identification list. The subject identification list shall only be available at the site, both throughout and after the study.

5.5 Withdrawal of Subjects

Each subject shall be advised in the Informed Consent Form that the subject has the right to withdraw from the study at any time, for any reason, without prejudice. Subjects may also be discontinued from this study if the Investigator determines that it is in the subject's best interest to do so, and may be withdrawn at the Investigator's discretion at any time.

The withdrawal criteria are:

- **Medical reasons:** If the subject suffers from a medical condition that in the judgement of the Investigator makes it medically necessary to withdraw the subject. The specific rationale for Investigator-initiated withdrawal of a subject for medical reasons shall document the specific condition for withdrawing the subject.
- **Withdrawal of informed consent:** A subject can withdraw their consent to participate in the study at their own request or be withdrawn from participation in the study at the request of their legally authorised representative at any time for any reason.
- **Lost to follow-up:** If a subject does not return for a scheduled visit, reasonable effort shall be made to contact that subject, e.g. call three times at different hours and leave messages if applicable before declaring the subject lost to follow-up.
- **Other:** Examples of other reasons for withdrawal may be failure to comply with protocol requirements or to complete the protocol-specified evaluations.

The reason and date for withdrawal shall be documented in the eCRF. When possible, an explanatory comment shall be added in the study termination module/pages to further explain the reason for withdrawal. If withdrawal of a subject occurs during a regular study visit, the eCRF for that specific visit shall be completed as far as possible together with the study termination eCRF module.

If withdrawal of a subject occurs between regular study visits the subject should when possible (irrespective of the reason for withdrawal) be scheduled for a termination visit. In these cases the eCRF for the early termination visit should be completed. The subject will need to follow the same requirements for the final visit.

If a subject is withdrawn from the study, all data collected until the time of withdrawal will be used in the analyses.

A withdrawn or discontinued subject must not be replaced or re-entered into the study.

If an AE which, according to the Investigator's assessment, is related to the use of any of the study products and is still ongoing at the time of the withdrawal, such events shall be

	
Title 43CH1626 Clinical Study Protocol
	
Doc id MA-33281

--	--	-----------------------------------

followed-up after the last study visit until resolved, assessed as chronic or stable, or for at least three months.

6 Study Products

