4.6 Concomitant Medication, Treatment, and Procedure

Except as noted below, concomitant medications or other treatments or procedures may be utilized when the PI or his/her authorized designee considers it medically necessary.

Information regarding any use of concomitant medications, including over-the-counter medications administered during the study is to be recorded in the eCRF. The generic name or the trade name of all concomitant medication or a description of the procedure and the reason for its use shall be documented in the eCRF.

The following medications, treatments, and procedures are restricted or prohibited during the study:

- Anticoagulants or inhibitors of platelet aggregation (*e.g.* aspirin or other non-steroidal anti-inflammatory drugs [NSAIDs]), Omega-3, or Vitamin E should not be used within two weeks before treatment to avoid increased bruising or bleeding at injection sites.
- Lidocaine should be used with caution in patients receiving other local anesthetics or agents structurally related to amide-type local anesthetics *e.g.*, certain antiarrhythmics, since the systemic toxic effects can be additive.
- Concomitant treatment with chemotherapy, immunosuppressive agents, immunomodulatory therapy (*e.g.*, monoclonal antibodies) is prohibited.
- Long term concomitant treatment with systemic or topical (facial) corticosteroids is prohibited (inhaled corticoids are allowed). Corticosteroids should be used with caution and should be adjudged as necessary by the Investigator.
- Use of systemic or topical (facial) retinoic acid is prohibited.
- Facial tissue augmenting therapy, contouring or revitalization treatment with fillers, lifting threads, permanent implant, mesotherapy, radiofrequency, ultrasound, cryotherapy, fat-injection, neurotoxin, laser or light treatment, chemical peeling or dermabrasion below the level of the lower orbital rim are prohibited.
- Planned surgery including aesthetic facial surgical therapy or facial liposuction, sinus surgery or dental root surgery, or tattoo in the area to be treated is prohibited.
- Participation in any other clinical study is prohibited

If a subject has used any of the above prohibited medications or performed any of the above prohibited procedures, a protocol deviation will be documented. The subject should continue in the study for the scheduled follow-up visits.

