10.6 Handling of Missing Data

Number of missing values will be summarized and reported as appropriate.

Different assumptions regarding the missing data will be used. For the primary effectiveness analysis, missing values in the FAS will be assumed to be missing due to lack of effect. Therefore missing data up to the Month 6 visit will be imputed using the baseline observation carried forward (BOCF) method. As an alternative approach, missing data will be assumed to be unrelated to treatment effect. To impute data under this assumption, missing data up to the Month 6 visit will be imputed using the hot deck method. More details will be given in the SAP. Both of these alternatives will estimate the effectiveness of the treatment policy (irrespective of use of unallowed treatments, procedures, or medications) rather than the true, clinical treatment effect.

To obtain an estimate of the true, clinical treatment effect, the primary effectiveness analysis will be performed using the PP.

All other endpoints will be analysed on available data, i.e. no imputations will be done.

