### 2.4.2 Handling of missing data

[figure not shown]
Number of missing values will be summarized and reported as appropriate.

Different assumptions regarding the missing data will be used. For the primary effectiveness analysis, missing values in the FAS will be assumed to be missing due to lack of effect. Therefore missing data up to the Month 6 visit will be imputed using the baseline observation carried forward (BOCF) method. As an alternative approach, missing data will be assumed to be unrelated to treatment effect. To impute data under this assumption, missing data up to the Month 6 visit will be imputed using the hot deck method (Table 9-2). Both of these alternatives will estimate the effectiveness of the treatment policy (irrespective of use of disallowed treatments, procedures, or medications) rather than the true, clinical treatment effect.

To obtain an estimate of the true, clinical treatment effect, the primary effectiveness analysis will be performed using the PP population.

All other endpoints will be analyzed on available data, i.e. no imputations will be done.

[figure not shown]
CCI

[figure not shown]
 GALDERMA	Title SAP, 43CH1626, Restylane Volyme Midface	Doc id MA-35135
--	--	---------------------------

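### Withdrawal for non-compliance (Protocol 5.5) is not reconciled with continued follow-up after prohibited treatment (4.6), so Month 6 scores that the treatment-policy analysis needs can be lost and become BOCF non-responses

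*Protocol*

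**What the plan says.** - **Withdrawal (Protocol 5.5).** Under the category Other, the list of withdrawal criteria gives as an example "failure to comply with protocol requirements or to complete the protocol-specified evaluations". The same section says that subjects "may be withdrawn at the Investigator's discretion at any time". Data collected up to withdrawal are used, and a withdrawn subject is neither replaced nor re-entered.
- **Prohibited treatments (Protocol 4.6).** The rule opens "If a subject has used any of the above prohibited medications or performed any of the above prohibited procedures". It then requires a documented deviation and adds: "The subject should continue in the study for the scheduled follow-up visits".
- **What the analysis estimates (Protocol 10.6, SAP 2.4.2).** The protocol says of BOCF and hot deck: "Both of these alternatives will estimate the effectiveness of the treatment policy (irrespective of use of unallowed treatments, procedures, or medications". The SAP repeats that they "estimate the effectiveness of the treatment policy (irrespective of use of disallowed treatments, procedures, or medications".
- **Missing data (Protocol 10.6).** For the primary analysis, "missing data up to the Month 6 visit will be imputed using the baseline observation carried forward (BOCF) method". The reason given is that missing values are taken to reflect lack of effect. The SAP's Table 9-1 applies BOCF to the FAS row.
- **Response (Protocol 3.2.1).** A responder improves by at least 1 MMVS point on both sides, as rated by the blinded evaluator.

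**The concern.** Using a prohibited procedure is one way of failing to comply with the protocol, so 5.5 and 4.6 both cover that subject. One permits the end of participation and the other keeps the subject in the visit schedule. Neither section refers to the other, and no visible text says which prevails.

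This reaches the primary endpoint. A treatment-policy estimate needs the Month 6 score that was actually observed in subjects who used something disallowed. If such a subject is withdrawn first, the score does not exist, and carrying baseline forward gives a change of zero, which is always a non-response. The lack-of-effect rationale for BOCF does not describe a subject who was removed for a deviation. Two sites could therefore treat identical subjects differently, one entering an observed score and the other an imputed failure. The treating investigator and the subject both know the assignment (Protocol 4.4.2), so the decision to withdraw is not protected by blinding.

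**Working it through.** **Inputs from the documents**
- Group B: 111 Treatment, 37 Control (Protocol synopsis). 111 + 37 = 148, the stated total.
- Planning response rates: 70% Treatment and 35% Control (Protocol 10.10, SAP 2.7). Planned difference: 70 − 35 = 35 points.
- A BOCF value is always a non-response (Protocol 3.2.1 with 10.6).

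**Inputs not in the documents.** No rate of withdrawal for non-compliance is given, nor any response rate after a disallowed treatment. Both are assumed below and shown as ranges. Alpha is redacted; two-sided 0.05 is assumed wherever power is quoted.

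**Formula.** In one arm, let p be the response rate of the other subjects, w the share withdrawn before Month 6 for non-compliance, and r the response rate those subjects would have shown if followed.
- Rate under BOCF: (1 − w) × p
- Rate if followed, as treatment policy requires: (1 − w) × p + w × r
- Loss in that arm: w × r

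Error in the difference (Treatment minus Control) = w_C × r_C − w_T × r_T. A positive value favours the product.

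**Per subject.** One would-be responder lost lowers the Control rate by 1/37 = 2.7 points and the Treatment rate by 1/111 = 0.9 points.

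**Control-only withdrawal (assumed w_T = 0, p_C = 35%)**

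| w_C | r_C | BOCF difference | Difference if followed | Inflation |
|---|---|---|---|---|
| 0% | any | 35.0 | 35.0 | 0 |
| 5% | 35% | 36.75 | 35.0 | 1.75 |
| 5% | 70% | 36.75 | 33.25 | 3.5 |
| 5% | 100% | 36.75 | 31.75 | 5.0 |
| 10% | 35% | 38.5 | 35.0 | 3.5 |
| 10% | 70% | 38.5 | 31.5 | 7.0 |
| 10% | 100% | 38.5 | 28.5 | 10.0 |

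For example, with w_C = 10% and r_C = 70%, the BOCF Control rate is 0.90 × 35 = 31.5%. The followed rate is 31.5 + 0.10 × 70 = 38.5%. The differences from 70% are 38.5 and 31.5 points, 7.0 apart.

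**Other patterns**
- Treatment-only withdrawal at 5% or 10% with r_T = 70%: the difference falls from 35.0 to 31.5 or 28.0 points, against the product.
- 10% of Controls and 5% of Treatment withdrawn, with the same r of 70-100% in both arms: (10% − 5%) × r = 3.5 to 5.0 points of inflation.
- Equal w and equal r in both arms: error 0.

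**Power.** At 111/37 with 70% against 35%, power is about 97% (normal approximation). With Control-only use at 10% and those subjects followed up, it is about 93% at 70% against 38.5%, and about 87% at 70% against 41.5%.

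**The case against.** The strongest reply is that 4.6 is specific and 5.5 is general and permissive, so the specific rule governs and a site would have to disregard 4.6 to cause the problem. That is a sensible reading, but neither section states it, and 5.5 also allows withdrawal at the investigator's discretion. The direct conflict is still narrow. It covers prohibited medications and procedures only, because 4.6 says nothing about missed evaluations or other non-compliance. It affects the primary endpoint only when withdrawal comes before Month 6.

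A reader might infer that the conflict inflates the effect, because untreated Controls have more reason to seek another procedure, and that the inflation is 7-10 points. The documents do not support that. Controls are offered the study treatment at Month 6 (4.1), inclusion criterion 3 requires willingness to abstain, and exclusion criterion 23 screens out those unlikely to avoid other facial cosmetic treatments. The 7-10 points assume that 10% of Controls and nobody in the Treatment Group are withdrawn, and that 70-100% of those Controls would have responded. The list in 4.6 includes retinoids, corticosteroids, neurotoxin, peels and laser, which need not restore volume, and Protocol 2.3 states that no filler intended for this indication was available in China.

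Two safeguards exist but do not close the gap. Where possible, an early-termination visit is held whatever the reason for withdrawal, and it includes the blinded MMVS. No visible text assigns that score to Month 6; part of SAP 2.4.2 is redacted and may do so. The hot-deck analysis would not score these subjects as automatic failures and could show that BOCF matters, but it imputes as if missingness were unrelated to effect and cannot replace an observed score.

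**Conclusion.** The point holds in a limited form. Sections 5.5 and 4.6 give unreconciled instructions for a subject who used a prohibited treatment. Applying 5.5 before Month 6 removes the observation on which the stated treatment-policy estimate depends and replaces it with a non-response. The direction of bias is not determined: it is w_C × r_C − w_T × r_T. Under the planning rates, Control-only withdrawal of 0%, 5% or 10% with response of 35-100% inflates the difference by 0, 1.8-5.0 or 3.5-10 points. Treatment-arm withdrawal works against the product, and balanced withdrawal and response cancel. All withdrawal and post-deviation response rates here are assumptions.

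A reader might also infer that the trial's conclusion is at risk. The figures do not show that: with about 97% power at the planning values, and about 87% in the most extreme followed-up case above, the size and meaning of the estimate are more exposed than the significance test. This is a cheap improvement to make, not a fatal flaw.

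**What to change.** Reconcile Protocol 5.5 with 4.6. State that non-compliance alone, whether use of a prohibited treatment or a missed evaluation, does not end study follow-up, that the deviation is recorded, and that the Month 6 blinded MMVS is still obtained. The missed-evaluation part goes beyond the direct conflict; it is included because it avoids missing data at no extra design cost.

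Leave consent withdrawal, loss to follow-up, medical reasons and the investigator's discretion to act in the subject's best interest as they stand. A closed list of withdrawal reasons is not needed. The change concerns data collection only and does not touch treatment decisions.

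Cost: protocol wording and a few more visits for non-compliant subjects. The Month 6 visit and its blinded assessment are already scheduled for both groups.

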6.1 Investigational Product

Restylane Volyme is a sterile, biodegradable, transparent gel of non-animal cross-linked hyaluronic acid with the addition of lidocaine hydrochloride 3mg/mL. The gel is supplied in a 1 mL prefilled plastic syringe. The contents of the syringe are sterilized using moist heat. The syringe is packaged individually in a blister, with two 27G x ½" Ultra thin wall needles.

6.2 Reference Product

Not applicable.

6.3 Additional Products and Material

The study product is supplied in sterile 1 mL syringes, with two 27G x ½" Ultra thin wall needles for injection. Any other materials will be supplied by the site.

6.4 Packaging, Labelling and Storage

Restylane Volyme is manufactured by Q-Med AB, Uppsala, Sweden who will supply the study products. Restylane Volyme will be used for the study.

The syringes are labelled with name of the product, name of the manufacturer (Q-Med AB). The syringes in its blister are packed in a carton. The carton will be labelled in local language, specifying the protocol number, lot number, expiry date and that the product is to be used for clinical studies exclusively.

The study products should be stored at a temperature up to 25°C and protected from sunlight and freezing. Opened syringes should not be re-used. Accountability will be performed as specified in section 6.5.

6.5 Product accountability

The study product will be released to the PI or his/her authorised designee after study approvals have been received from the IEC and the CTA has been signed by all parties.

The PI must ensure that the study product is kept in a secure location, with access limited to those authorised by the PI.

The study product must be traceable from the manufacturer to its use in subjects until return or disposal. It is therefore important that the PI maintains accurate product accountability records, i.e. documentation of the physical location of all study product, deliveries, and return of study product between the Sponsor or a third-party vendor and the PI, and documentation of administration of product to the subject. A shipping record shall be kept of all study products received from the Sponsor; including the product name, date received, batch number, expiration date, and amount received. In addition, dispensing logs shall be maintained including the product name, dispense date, the number of syringes

 GALDERMA	Title 43CH1626 Clinical Study Protocol	Doc id MA-33281
--	--	---------------------------

used, the number of syringes left in stock, and the subject receiving study product. A log for accountability procedure is provided by the Sponsor.

When the study is completed, all unused or expired study product at each study site shall be returned to the Sponsor or a third-party vendor for destruction. Any malfunctioning study products shall be reported as described in Section 8.5.3.

Product deliberately or accidentally destroyed during shipment or at a study site shall be accounted for and documented. Used syringes, disposable needle, and any opened unused material must be discarded immediately after the treatment session and must not be reused due to risk for contamination of the unused material and the associated risks including infections according to standard procedures at the site. Disposal of hazardous material, i.e. syringes and needles must conform to applicable laws and regulations. The study product must not be used outside the study.

6.6 Treatment

6.6.1 Treatment Procedure

The subjects will be informed about the indications, expected result, precautions and potential AEs.

Local anesthetics (topical, infiltrative, or regional blocks) before the treatment will be used at the discretion of the treating Investigator. Injection procedures are associated with a risk of infection. Aseptic technique and standard practice to prevent cross-infections should be observed at all times including the use of disposable gloves during the injection procedure. The subject should not wear make-up on the day of treatment, if make-up was already applied this must be completely removed prior to any injection. The treatment site should be thoroughly cleaned at least twice with a suitable antiseptic solution.

To avoid breakage of the needle, no attempt to bend or otherwise manipulate it before or during treatment is recommended. Before injecting, the air should be removed by pressing the rod carefully until a small droplet is visible at the tip of the needle. Aspiration prior to injection in order to avoid accidental intravascular injection is recommended. Injection should stop just before the needle is pulled out from the skin to prevent material from leaking out from the injection site. Excessive pressure must not be applied at any time during injection. If resistance is encountered the needle should be partially withdrawn and repositioned or fully withdrawn and checked for function.

[figure not shown]
Restylane Volyme should be injected into supraperiosteal zone or subcutis in the midface.

Restylane Volyme will be administered inferior to the maxillary prominence, superior to the plane of nasal alae, including the area from the lateral canthus to the medial canthus and lateral to the nose on the subject's right and left sides (Figure 2). If Restylane Volyme is injected too superficially this may result in visible lumps and/or bluish discolouration. Investigators will be instructed to use the amount of dermal filler necessary to achieve an optimal aesthetic result. A touch-up treatment may be performed 4 weeks after the initial treatment if optimal midface augmentation has not been obtained. Defects should be fully corrected, but not overcorrected.

 GALDERMA	Title 43CH1626 Clinical Study Protocol	Doc id MA-33281
--	--	---------------------------

Care should be taken to avoid intramuscular injection. This can often be recognized by an increased force of injection required compared to subcutaneous injection. Care should also be taken to avoid excess deposition of material into individual areas. After each injection, the area should be observed to assess the degree of enhancement and the uniformity of the implant. The area should be gently palpated to ensure an even deposition of the implant. Palpated “skip areas” should be treated with additional implant material or by gentle massage/kneading of the area until a uniform implant is palpable.

Figure 2. Injection Area

Information regarding the local anaesthetic used, injection technique, depth of injection and volume used per side will be recorded.

